Washington) will be used to assess home ambulatory function. Previous research by our group has validated this device for patients with PD and has shown that step count as measured by this device is highly correlated with disease severity in PD (85). Subjects will wear the SAM at home over 48 hours while performing their usual daily routines (removing it during bathing and sleep). Recording will be done on the days that immediately precede or follow the on-site clinical testing of the other outcome measures. Placement of the SAM will be taught to the subject on site during their first testing session. Individual calibration will be done based on each subject's height and gait (e.g. subjects will perform a 30-foot walk while an examiner records time and number of steps without the SAM). Two variables will be measured: mean step count per day and maximal number of steps per hour.

Statistical Analysis Plan (SAP):

The data from the study will be entered into a dataset and validated by the investigators. Descriptive statistics will be calculated for all variables using SAS version 9.1 (SAS institute, Cary, N.C.). Exploratory data analyzes will be performed to check the data for extreme values and to test for normality (Kolmogorov-Smirnov test). If our data is not normally distributed, we will try conventional normalizing and/or variance stabilizing transformations to obtain something close enough to a Gaussian distribution to enable the use of parametric statistics. A two-tailed $p < 0.05$ will be considered indicative of a significant result. Below is a description of the statistical analyses to test each hypothesis of this study:

Hypothesis I: The combined intervention TAEX + TCOG group will show greater improvement in EF than either group alone.

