EF performance will be stratified into domains and standardized as composite scores using z-score transformation. In addition, an overall composite variable will be derived from the ANAM battery, representing an Index of Cognitive Efficiency (ICE). The ICE will be derived by weighting throughput scores from the individual ANAM tests and then combining them into a single score reflecting overall performance on the test battery. The weighting will be done so that each score contributes equally to the overall index with higher scores indicative of better test performance. This method has been used in previous studies to combine data in an efficient manner to look at cognitive performance over time (86). Our dependent variables are: 1) a total z-score for each EF domain and 2) the ICE.

Each dependent variable will be evaluated with a parametric Mixed Models Repeated Measures Analysis of Variance (ANOVA), with Group as the between factor (TAEX, TCOG, TAEX+TCOG) and Time as the within factor (pre-test, post-test). Therefore, each intervention group will be compared against each other, and against the baseline phase (i.e. those undergoing delayed entry). We will adjust for potential confounding variables such as age, educational level, and behavioral variables (depression, fatigue, apathy and self-efficacy) by including these in the analysis as covariates. Post-hoc pair-wise comparisons will be done using Tukey's Honestly Significant Difference with an $\alpha = 0.05$ as the experiment-wise error rate. An intention-to-treat analysis paradigm will be used to account for missing data (e.g. subjects from whom we have obtained data at baseline, but who later drop out). The data collected from these subjects along with those who completed the study will be combined using multiple imputation. These analyses will be performed using the SAS procedures PROC MI and PROC MIANALYZE and

will provide insight into the effectiveness of our interventions.

Hypothesis II: The combined intervention TAEX + TCOG group will show greater improvement in DT than either group alone.

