Our dependent variables on DT performance are: 1) the number of words generated per second, 2) spatiotemporal gait parameters including walking speed, stride length, cycle time, and variability of cycle time, 3) Cognitive Cost and 4) Gait Cost. Each dependent variable will be evaluated with a parametric Mixed Models Repeated Measures Analysis of Variance (ANOVA), with Group as the between factor (TAEX, TCOG, TAEX+TCOG) and Time as the within factor (pre-test, post-test). Therefore, each intervention group will be compared against each other, and against the delayed entry phase. Similar to the analysis described under Hypothesis I, we will adjust for potential confounding variables, run a Tukey's Honestly Significant Difference post-hoc test, and perform an intention-to-treat analysis for Hypothesis II.

Hypothesis III: Improvement in DT performance will be associated with improvement in IADLs function.

Our IADL measures are: 1) OARS IADLs, 2) Timed IADLs and 3) daily activity as measured by the SAM. To test Hypothesis III, these measures will be converted into change scores. Therefore our dependent measures are: 1) OARS change scores (post-test – pretest), 2) Timed IADLs (post-test – pretest), 3) SAM change scores (post-test – pretest). These measures will be correlated with DT performance measures, also represented as change scores.

Correlations between OARS IADLs change scores and DT change scores will be calculated using non-parametric statistics, Spearman Correlation Analysis, because OARS produces rank-ordered data. Correlations between Timed IADLs change and DT change, as well as correlations between SAM change and DT change will be calculated using parametric statistics: Pearson Product Moment Correlation Analysis.

Secondary analyses:

In order to investigate whether EF improvements are associated with cardiopulmonary fitness improvements, we will run Pearson Product Moment Correlations. Correlated variables will be: 1) change in EF performance (z-scores and ICE) where change is calculated as pre-test – post-test, and 2) change in cardiopulmonary fitness measures (Peak VO₂ max, METs, 6 min walk test time) where change is calculated as pre-test – post-test.

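### The planned Group-by-Time ANOVA compares arms on raw change and makes no use of the outcome's own pre-test as a covariate: valid under random allocation, but less precise than the collected data allow

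*Combined protocol and SAP*

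**What the plan says.** The Statistical Analysis Plan gives one model for the executive function (EF) outcomes under Hypothesis I and repeats it for the dual-task (DT) outcomes under Hypothesis II. The method is given as "Each dependent variable will be evaluated with a parametric Mixed Models Repeated Measures Analysis of Variance (ANOVA"). In both places the model's factors are then set out in the same terms: "with Group as the between factor (TAEX, TCOG, TAEX+TCOG) and Time as the within factor (pre-test, post-test").

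Both hypotheses concern improvement. Hypothesis I reads "The combined intervention TAEX + TCOG group will show greater improvement in EF than either group alone", and Hypothesis II reads "The combined intervention TAEX + TCOG group will show greater improvement in DT than either group alone".

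The covariates are introduced with "We will adjust for potential confounding variables such as age, educational level, and behavioral variables (depression, fatigue, apathy and self-efficacy"). Hypothesis II carries this over: "Similar to the analysis described under Hypothesis I, we will adjust for potential confounding variables". The outcome's own pre-test is not listed.

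On testing, the plan states "A two-tailed $p < 0.05$ will be considered indicative of a significant result" and "Post-hoc pair-wise comparisons will be done using Tukey's Honestly Significant Difference". It does not name the Group-by-Time interaction or say which means Tukey's procedure compares. Dropouts with baseline data are handled by multiple imputation. Neither an analysis of covariance (ANCOVA) on the pre-test nor a model with a common pre-test mean appears anywhere.

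**The concern.** With two visits and separate arm means at each, the Group-by-Time contrast is the difference between arms in mean change. That amounts to fixing the slope of post-test on pre-test at 1. When the pre/post correlation is below 1, this slope is usually too steep, and the contrast carries noise that the pre-test could have removed.

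The stake is precision on the EF and DT comparisons among three active arms. Differences between active arms may be modest, and Tukey's procedure makes each pairwise comparison more demanding. The pre-tests are collected anyway, so the lost precision could be recovered without new data.

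**Working it through.** **Inputs from the documents.** The model, hypotheses, covariates, two-sided 0.05 level and Tukey comparisons are as set out above. The text gives no sample size, power, effect size, SD, pre/post correlation or method of allocation, so there is no planned figure to reproduce.

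**Assumptions.** Random allocation; pre/post correlation rho from 0.3 to 0.9; equal SD (s) at both visits unless stated; n per arm.

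**Step 1: the planned contrast is a raw change difference.** In one simulated data set (three arms of 20, slope 0.7), the two interaction estimates from a random-intercept mixed model were 0.04954 and 0.55421, each with SE 0.234. Ordinary regression of post minus pre on Group gave the same values. Adding a time-invariant covariate as a main effect, which is how age or education would ordinarily enter, changed neither estimates nor SEs. ANCOVA on the same data gave SE 0.221.

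**Step 2: variances of a pairwise contrast.**
- Planned: 2(1 − rho) · s² · (2/n)
- Adjusted for pre-test: (1 − rho²) · s² · (2/n)
- Ratio, adjusted to planned: (1 − rho)(1 + rho) / [2(1 − rho)] = (1 + rho)/2

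The confidence interval narrows by 1 − √ratio. The planned analysis needs 1/ratio − 1 more participants for equal precision. If the planned contrast has 80% power, the adjusted one has Φ(2.802/√ratio − 1.960), where 2.802 = 1.960 + 0.842. At rho 0.5 this is Φ(2.802/0.866 − 1.960) = Φ(1.275) = 0.90.

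| rho | 2(1−rho) | 1−rho² | Ratio | CI narrower by | Extra participants, planned analysis | Power, if planned has 80% |
|---|---|---|---|---|---|---|
| 0.3 | 1.40 | 0.91 | 0.65 | 19% | 54% | 93.5% |
| 0.5 | 1.00 | 0.75 | 0.75 | 13% | 33% | 90% |
| 0.7 | 0.60 | 0.51 | 0.85 | 8% | 18% | 86% |
| 0.8 | 0.40 | 0.36 | 0.90 | 5% | 11% | 84% |
| 0.9 | 0.20 | 0.19 | 0.95 | 2.5% | 5% | 82% |

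The power figures are for a single pairwise contrast without Tukey adjustment.

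**Step 3: small samples.** Estimating the slope costs a factor of about 1 + 1/(N − 5) for three arms and total N. With an assumed 20 per arm (N = 60) this is 1.018, giving 0.76 and 0.87 at rho 0.5 and 0.7. A simulation of 20,000 trials gave 0.77 and 0.87, and 0.96 at rho 0.9. The gain is cancelled when (1 + rho)/2 · [1 + 1/(N − 5)] = 1, that is, at rho of about 0.92 for N = 30 and 0.96 for N = 60.

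**Step 4: unequal SDs.** If the post-test SD is k times the pre-test SD, the planned variance exceeds the adjusted one, before the slope-estimation cost, by an amount proportional to (1 − k·rho)². This is zero only when k·rho = 1. Over rho 0.3 to 0.9 the ratio runs from 0.50 to 0.64 at k = 0.8, and from 0.76 to 0.997 at k = 1.2.

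**Step 5: chance imbalance.** A one-SD chance difference in pre-test means is √(2/n) · s, and it shifts the planned contrast by (1 − rho) times that. At rho 0.5 and n = 20 the shift is 0.5 × 0.316 = 0.158 SD, and its square is 0.025. The excess variance from Step 2 is (1.00 − 0.75) × 0.1 = 0.025. The two are the same quantity.

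**The case against.** The strongest reply is that nothing here is an error. The hypotheses ask about greater improvement, and a difference in change answers that directly. With randomised arms the contrast is unbiased and keeps its type I error. That stands, and it limits the point to efficiency.

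The size is also uncertain. The domain z-scores and the overall ANAM index are composites, so a high rho is plausible, and at 0.9 the gain is only 5% of variance. Other outcomes may be noisier, such as reaction times formed by subtraction or cycle-time variability from a short walk, but that is inference. The documents settle neither case.

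Four stronger readings are tempting, and the documents do not support them:
- **That every planned comparison is a raw change difference.** The plan does not say which means Tukey's procedure compares. Behavioural covariates entered at both visits would make the contrast an adjusted change, though still not adjusted for the outcome's own pre-test. The comparison with the delayed-entry phase is a different contrast, not covered by this calculation.
- **That adjustment can never be less precise.** This holds in large samples only. Step 3 shows the break-even points.
- **That chance pre-test imbalance adds a bias.** Under random allocation it is the same variance loss expressed differently (Step 5).
- **That pre-test-only participants are lost under the present plan.** Multiple imputation already brings them in.

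Two replies do not remove the point. The covariate list is open-ended, but the pre-test cannot sensibly be a covariate while it is also a response in the same model. Multiple imputation fills in missing post-tests but leaves the analysis model unchanged.

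**Conclusion.** The point holds as a loss of efficiency in the comparisons among the three intervention arms, with improvement read as the Group-by-Time contrast. With equal SDs, the saving from adjustment runs from about 35% of the contrast variance at rho 0.3 to 5% at rho 0.9, slightly less in small samples. It can nearly vanish when the post-test SD is larger than the pre-test SD and rho is high. The rho values, the SD ratios and the 20 per arm are all assumptions.

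The conclusion also depends on random allocation, which the text does not describe. Without it, adjusted and change-score analyses need not estimate the same effect, and forcing a common pre-test mean would not be justified. The change is worth making because it costs little, and not because the planned test is invalid.

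**What to change.** For the comparisons among the three intervention arms, analyse each EF and DT outcome in one of two ways:
- ANCOVA of the post-test on Group and that outcome's own pre-test; or
- a mixed model with both visits as responses and one pre-test mean common to all arms.

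Choose one in advance, because the two can differ when post-tests are missing. Name the adjusted between-arm difference at post-test as the tested contrast and apply Tukey's procedure to those differences. The listed covariates and the multiple imputation can stay.

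State that the analysis relies on random allocation to the three arms, and describe that allocation. Keep the delayed-entry comparison as a separately specified contrast, saying which measurement serves as its baseline.

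The cost is a sentence and a changed model statement for the three-arm comparison, one on allocation, and a short specification of the delayed-entry contrast. No new data are needed. Under ANCOVA the analysis gives up one degree of freedom for the slope.

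### Hypotheses I and II claim the combined arm beats both single arms, but the only stated test is post-hoc all-pairs Tukey, which is valid but less powerful than such a claim needs and comes with no success rule

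*Combined protocol and SAP*

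**What the plan says.** The SAP states Hypothesis I as "The combined intervention TAEX + TCOG group will show greater improvement in EF than either group alone" and Hypothesis II as "The combined intervention TAEX + TCOG group will show greater improvement in DT than either group alone". Each is a statement about improvement, and each sets the combined arm against two comparators.

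Every dependent variable gets a mixed-model repeated-measures ANOVA with three groups and two time points. The follow-up under Hypothesis I is "Post-hoc pair-wise comparisons will be done using Tukey's Honestly Significant Difference" "with an $\alpha = 0.05$ as the experiment-wise error rate". Hypothesis II repeats it: the analysts will "run a Tukey's Honestly Significant Difference post-hoc test, and perform an intention-to-treat analysis for Hypothesis II". The general significance rule is "A two-tailed $p < 0.05$ will be considered indicative of a significant result".

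Two other statements bear on the choice of method. Aims 1 and 2, in the Outcomes Testing section, ask for a three-way comparison of the interventions. Under both hypotheses the SAP also says that the groups will be compared with one another and with a delayed-entry phase. No section names the two combined-versus-single contrasts as the test of the hypothesis, says whether one or both must be significant, or says that the pairwise comparisons are of change.

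**The concern.** A claim that the combined arm is better than each single arm is a conjunction. When both tests must succeed, each can be run at 0.05 and the chance of a false joint claim still does not exceed 0.05 (the intersection-union principle). Tukey's higher limit protects a different family, namely any false statement among all three pairs. Applying it to the conjunction raises the bar on both tests at once, and the probability of clearing both falls more than the probability of clearing either.

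At stake is the chance of confirming the two headline hypotheses when they are true. A lesser matter is clarity: with no success rule and no statement that the contrasts are on change, the SAP leaves the analyst to decide after the fact what counts as support.

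**Working it through.** **Inputs from the SAP.** Three groups, hence three pairs; two-sided 0.05; experiment-wise 0.05 for Tukey within one dependent variable.

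**Assumptions, because the documents do not state them.** Equal arms; large-sample normal statistics; the combined arm better than both single arms by the same amount; each contrast alone has 70%, 80% or 90% power at two-sided 0.05.

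**1. The plan's own figure.** Tukey's limit for three groups is the 0.95 quantile of the studentized range divided by √2, which is 2.344. The two-sided level per pair is 0.0191, and the error over all three pairs is 0.0500 (simulation: 0.0500). The stated experiment-wise rate is reproduced. The limit without adjustment is 1.960. With 57 df (20 per arm, an illustration only) the two limits are 2.41 and 2.00.

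**2. Correlation of the two contrasts.** Both use the combined arm. With equal arms each contrast has variance 2σ²/n and their covariance is σ²/n, so the correlation is 0.5.

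**3. Joint power.** The expected z for a contrast with 80% power is δ = 1.960 + 0.842 = 2.802. The probability that both exceed a limit c is Φ₂(δ − c, δ − c; 0.5). For the step-down (largest pair at 2.344, then the rest at 1.960) it comes from simulation.

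| Power of each contrast alone at 0.05 | Both succeed, Tukey | Both succeed, 0.05 each | Both succeed, step-down |
|---|---|---|---|
| 70% | 39% | 56% | 53% |
| 80% | 53% | 69% | 67% |
| 90% | 71% | 83% | 82% |

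**4. The same in sample size.** For 80% joint power, the numbers per arm at 0.05 each versus Tukey are 79 vs 99 for a standardised difference in change of 0.5, 31 vs 39 for 0.8, and 20 vs 25 for 1.0. The ratio is about 1.25 throughout.

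**5. Error of the joint claim.** The worst case is one contrast truly null and the other very large. The chance of a false claim in favour of the combined arm is then 1 − Φ(c): 0.025 at c = 1.960 and 0.0095 at c = 2.344. Tukey therefore does give a lower cap.

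**6. Validity of the step-down, and its limit.** With three means, either all are equal, and Tukey's limit protects the first step, or at most one pair is equal, and only one true null remains to be tested at 0.05. Simulated experiment-wise error is 0.050 under the full null and at most 0.050 under partial nulls. With a fourth mean this fails: if three means are equal and one is far away, the first step is passed almost surely and three true nulls are tested at 1.960, giving about 12.2% error.

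**The case against.** The strongest reply is that Tukey is the right tool for what the aims ask. Aims 1 and 2 want all three interventions compared, and the SAP says that the groups will be compared with one another. All-pairs Tukey at experiment-wise 0.05 is a standard, valid answer to that. This stands: the point is lost efficiency for the specific hypotheses, and Tukey can remain for the wider comparison.

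It is also fair that Tukey's stricter limit is not worthless. It holds the false both-arms claim at about 1% per outcome, and the SAP has several EF domain scores, the ICE and seven named dual-task variables with no adjustment across them. If seven outcomes were independent and each at its cap, the chance of at least one false claim would be 1 − 0.9905⁷ = 6.5% under Tukey and 1 − 0.975⁷ = 16.2% at 0.05 each. That is an illustrative worst case, but the margin given up should be acknowledged.

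Two stronger readings are tempting and are not supported.

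- A reader might infer that the plan accepts a win over one single arm as proof. If combined truly equals TCOG and both beat TAEX with 90% unadjusted power, Tukey shows combined better than TAEX about 82% of the time. But that pairwise finding is correct. It becomes an error only if reported as support for the full hypothesis, and no section says that one win is enough. The fault is that the rule is missing.
- A reader might infer that Tukey will be run on group means averaged over both visits. With a pre/post correlation of 0.5 or 0.8 this would multiply the expected z by √((1 − r)/(1 + r)) = 0.577 or 0.333, and 68% power at Tukey's limit would fall to 23% or 8%. But the hypotheses concern improvement, the model includes Time, and no section describes such a comparison. The text needs clarifying; the loss cannot be attributed to the plan.

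**Conclusion.** The point holds as one of efficiency and specification. The SAP's only test of two both-arms hypotheses is a valid all-pairs procedure whose limit is higher than the conjunction requires. On the assumption of equal arms and 80% power per contrast, this costs about 16 percentage points of joint power (69% to 53%), or about 25% more participants for the same joint power. Because the documents give no sample size, standard deviation or effect size, these are relative comparisons and say nothing about this trial's actual power.

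The result does not show inflated type I error within an outcome. It also assumes that the hypotheses mean better than both. If the sponsor meant that beating one single arm suffices, some adjustment is needed, but a Dunnett-type limit for two contrasts (2.212) would still be below Tukey's 2.344, and the SAP should say which meaning applies.

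**What to change.** Amend the post-hoc sentence under Hypothesis I and its reuse under Hypothesis II as follows.

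1. For each outcome, prespecify two Group-by-Time contrasts on change: combined minus TAEX and combined minus TCOG. Declare the hypothesis for that outcome only if both favour the combined arm at two-sided p<0.05.
2. For single-pair statements among the three intervention arms, including TAEX versus TCOG, keep Tukey or use the step-down: Tukey's limit for the largest pair, then 0.05 for the others. State that this holds experiment-wise 0.05 only for exactly three means.
3. Keep the delayed-entry comparisons outside that step-down family, and say how they will be tested.

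Contrast estimates and their standard errors can be pooled directly in PROC MIANALYZE, which the SAP already plans to use.

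The cost is SAP wording and two losses to be stated openly. Tukey simultaneous intervals would no longer match the decision rule for the hypotheses, and the cap on a false both-arms claim per outcome rises from about 1% to 2.5%. The change does not deal with multiplicity across the EF domains, the ICE and the dual-task variables, which needs its own rule.

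### Hypotheses I and II concern greater improvement, but the SAP does not name the contrast of pre-to-post change that would test them, and the usual outputs of its Tukey step compare levels

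*Combined protocol and SAP*

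**What the plan says.** All references are to the Statistical Analysis Plan part of the combined document.

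- **Hypothesis I**: "The combined intervention TAEX + TCOG group will show greater improvement in EF than either group alone". **Hypothesis II** has the same form: "The combined intervention TAEX + TCOG group will show greater improvement in DT than either group alone". Both are statements about change.
- **Outcomes for these two hypotheses** are scores at a visit: a z-score per executive-function domain and the ANAM efficiency index for Hypothesis I; word rate, gait parameters and the two dual-task costs for Hypothesis II.
- **Model**: a mixed-model repeated-measures ANOVA "with Group as the between factor (TAEX, TCOG, TAEX+TCOG) and Time as the within factor (pre-test, post-test").
- **Comparisons**: "each intervention group will be compared against each other, and against the baseline phase (i.e. those undergoing delayed entry"). Whether a level or a change is compared is not stated.
- **Pair-wise step**: "Post-hoc pair-wise comparisons will be done using Tukey's Honestly Significant Difference with an $\alpha = 0.05$ as the experiment-wise error rate". For Hypothesis II the plan is to "run a Tukey's Honestly Significant Difference post-hoc test" in the same way.
- **Change scores** are defined under Hypothesis III and under Secondary analyses, for correlations. They do not appear under Hypotheses I and II.

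**The concern.** The quantity in Hypothesis I is a difference of two differences: (post minus pre in TAEX+TCOG) minus (post minus pre in a single arm). In a two-visit factorial model that is a Group-by-Time contrast. The SAP does not name it.

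Tukey's procedure compares pairs of means. In this model the usual sets are:

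- three Group means, each averaged over pre-test and post-test. An advantage present only at post-test is halved, and any baseline difference counts in full;
- six Group-by-Time cell means, giving 15 pairs: post against post, pre against pre, pre against post within an arm, and mixed pairs across arms.

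No pair in either set is a difference in improvement. An analyst who takes the usual output could miss a real advantage of the combined arm. One who chooses among the sets after seeing the data has several answers to pick from. A significant gain in one arm beside a non-significant gain in another does not show that the first improved more.

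**Working it through.** **No figure to reproduce.** The documents give no sample size, power, effect size, SD, pre-post correlation or allocation method. From the documents come three arms, two visits and a Tukey experiment-wise level of 0.05. Assumed: equal arms of n = 15 to 40, SD 1 at each visit, correlation rho of 0.3 to 0.8, the combined arm's advantage d present at post-test only, no covariates and no dropout.

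**Step 1: difference and SD for one pair (combined against one single arm).**

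- Change: difference d, SD sqrt(2(1 - rho)), Tukey over 3 means.
- Group mean over visits: difference d/2, SD sqrt((1 + rho)/2), Tukey over 3 means.
- Post-test cell: difference d, SD 1, Tukey over 6 means.

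The noncentrality is the difference divided by SD times sqrt(2/n). Relative to change it is sqrt((1 - rho)/(1 + rho)) for Group means: 0.73 at rho 0.3, 0.58 at 0.5, 0.42 at 0.7 and 0.33 at 0.8. For the post-test cell it is sqrt(2(1 - rho)): 1.18 at rho 0.3, 1.00 at 0.5, 0.77 at 0.7 and 0.63 at 0.8.

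**Step 2: worked case, n = 25 per arm, rho = 0.7, d = 0.71** (chosen for 80% power on change). Here sqrt(2/n) is 0.283 and df, which is 3n minus 3, is 72. The critical value (studentized range divided by the square root of two) is 2.393 for 3 means and 2.928 for 6.

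- Change: 0.71 divided by the product of 0.775 and 0.283 gives 3.24 against 2.393; power 80%.
- Group mean: 0.355 divided by the product of 0.922 and 0.283 gives 1.36 against 2.393; power 16%.
- Post-test cell: 0.71 divided by 0.283 (SD is 1) gives 2.51 against 2.928; power 35%.

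**Step 3: over the assumed range**, with d reset each time so that Tukey on change has about 80% power per pair (noncentral t; simulation agrees closely):

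| rho | Group means | Post against post, six cells |
|---|---|---|
| 0.3 | 50% | 81% to 82% |
| 0.5 | 31% to 32% | 62% to 64% |
| 0.7 | 16% to 17% | 34% to 36% |
| 0.8 | 10% to 11% | 20% to 21% |

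At rho 0.5 the post-test cell has the same noncentrality as change and loses only through the larger critical value for six means. At rho 0.3 it loses nothing.

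**Step 4: effect of the planned covariates.** Suppose age, education and the behavioural scales explain 20% to 40% of total variance, all of it in the stable between-person part (an assumption). With n = 25, power for Group means rises from 31% to between 42% and 64% at rho 0.5 and from 16% to between 21% and 31% at rho 0.7. For the post-test cell it rises from 62% to between 75% and 89%, and from 35% to between 46% and 62%. The change contrast is essentially unaffected.

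**Step 5: equal true improvement, but a true baseline gap.** With n = 30 per arm, rho 0.7 and the combined arm 0.5 SD higher at baseline, at least one of its two comparisons is significant in 55% of simulated trials on Group means, 28% on post-test cells and 3.5% on change.

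**The case against.** The strongest reply is that the SAP does not say Tukey is applied to levels. A reader might infer from the factor list and the Tukey sentence that the plan tests mean levels instead of improvement. The text does not support that: it leaves the target open, and Tukey-adjusted contrasts of change are also allowed and best fit the hypotheses. With two visits, the Group-by-Time test in this model is equivalent to a one-way ANOVA on change, so the planned model can supply the right test. Nor does the SAP say that Tukey results decide the hypotheses, or that within-arm significance will be read as superiority. All of this stands, and it makes the defect an unspecified contrast, not a stated wrong one.

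It does not remove the need to specify. The interaction is not named, and an overall interaction test would not show that the combined arm beats each single arm. Pair-wise contrasts of change would still be required.

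A reader might also infer that a true advantage would mostly be missed. That holds for Group means at correlation 0.5 and above without covariates. It fails for post-test cell means at correlation 0.5 or below, and at n = 60 with d = 0.8 that comparison has 93% power whatever the correlation. The planned covariates reduce the losses further, as Step 4 shows.

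The false-positive rates in Step 5 need a systematic baseline gap. Chance imbalance under randomisation would not raise the error rate in this way. The supplied text describes no allocation method, so such a gap is neither shown nor excluded.

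**Conclusion.** The concern holds as a gap in specification with practical consequences. The SAP never identifies the comparison that answers Hypotheses I and II, and the usual outputs of its only pair-wise step contain no difference in improvement.

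If those outputs were used, power per pair would fall from 80% to about 31%, 16% and 10% on Group means at correlation 0.5, 0.7 and 0.8, and to about 62-64%, 34-36% and 20-21% on post-test cells, with no loss on the latter at 0.3. These figures rest on assumed n, SD, correlation and effect, and leave out covariates, imputation and the delayed-entry comparison. They show how much the choice can matter and do not predict this trial's power. The risk of favouring an arm that started higher is conditional on a true baseline difference.

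The SAP should be changed on this point, since naming the contrast gives a better answer at almost no cost.

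**What to change.** Replace the pair-wise sentence under Hypothesis I with wording such as:

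> Hypothesis I is tested by two Group-by-Time contrasts: (post minus pre in TAEX+TCOG) minus (post minus pre in TAEX), and the same against TCOG. They are estimated from the repeated-measures model in each imputed dataset and pooled with PROC MIANALYZE. The multiplicity adjustment is applied to these contrasts of change. Group means averaged over Time, and pre-to-post tests within an arm, are descriptive and are not used to judge the hypothesis.

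State under Hypothesis II that the same contrasts apply. If Tukey is kept, its family is the three pair-wise differences in change, with TAEX against TCOG as the third. Comparing post-test scores between arms with adjustment for the pre-test would be an acceptable alternative; the SAP should name one of the two.

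The cost is SAP wording and a few contrast statements in the existing SAS model, with no new data, patients or procedures. The one downside is that within-arm pre-to-post p-values can no longer be cited in support of the hypotheses.
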